6.1.4.8 Additional (Unscheduled) Follow-up Visits

Additional subject visits may occur as clinically warranted. The following information will be collected at such visits:

- Data regarding all adverse events including related laboratory tests results, ECG, details of any subsequent myocardial infarction, hospitalization, or repeat coronary angiography and results of such, if applicable. For suspected ischemic events, CK and CK-MB or Troponin (I or T) must be measured and 12 lead ECG obtained.
- Details of any subsequent coronary interventions (e.g., repeat PCI or CABG)

- Use and changes in chronic antiplatelet medication regimen. Data are collected for the duration of the trial
- Concomitant cardiac medication by category

6.1.5 Equipment to Be Used for Assessing the Clinical Variables

The Angiographic Core Lab will perform a qualitative and quantitative coronary analysis (QCA) (Pie Medical CAAS Workstation v. 5.11.2 Software) assessment of all target lesions preprocedure, post-procedure. Morphological characteristics (calcification, tortuosity, bifurcation, presence of thrombus), TIMI flow and blush will be assessed at baseline. Complications (no reflow, slow reflow, abrupt closure, new or worsening thrombus, distal embolization, perforation and dissection by NHLBI criteria) will be assessed intra-procedurally and at the end of the baseline procedure.

6.1.6 **Procedures for the Replacement of Subjects**

Discontinued subjects will not be replaced. De-registered subjects will not count towards the sample size of approximately 100 subjects and will not be included in the FAS but will be included in the safety analysis set and will be followed until resolution of any adverse events related to study procedures.

6.2 Investigational Device

6.2.1 Description of the Exposure to the Investigational Device

All subjects will have a single treatment which is the study stent implantation at baseline procedure. The stent will remain implanted throughout the duration of the follow-up period.

6.2.2 List of Any Other Medical Devices or Medication to Be Used During the Clinical Investigation

The stent implantation will be part of a standard cardiac intervention which includes accessory medical devices such as arterial sheaths, guidewires, guiding catheters, inflation devices, and other accessories. Standard medications such as heparin, contrast media, nitroglycerin, and relaxants are used. After the procedure, the subjects will receive DAPT for a minimum of 12 months (see Section 6.4.9.3) according to national guidelines and standard of care as well as other medications as prescribed to control other co-morbidities such as hypertension, hypercholesterolemia, and heart failure. All of these accessory medical devices and medications are approved to be on the market.

6.2.3 Number of Investigational Devices to Be Used

Each subject will receive at least one MedJ-01 stent. A subject can receive up to two stents per major coronary artery in a maximum of two major coronary arteries (A major coronary artery is defined as LAD, LCX, or RCA and their respective branches. The Ramus Intermedius is defined as a branch of the LCX). The total length of planned study stenting cannot exceed 100 mm.

6.3 Subjects

The Trial population will consist of approximately 100 male and female subjects undergoing PCI for angina (stable or unstable), silent ischemia, non ST elevation MI (NSTEMI), or recent ST elevation MI (STEMI >72 hours prior to enrollment and stable- subacute).

Complex lesions are allowed including calcified lesions (lesion preparation with scoring/cutting and rotational atherectomy (e.g.: Rotablator System) and Directional Coronary Atherectomy, DCA) are allowed), presence of thrombus that is non-occlusive and does not require thrombectomy, CTO, bifurcation lesions (except planned dual stent implantation), ostial RCA lesions, tortuous lesions, bare metal stent restenotic lesions, protected left main lesions. A maximum of two target vessels, with a maximum of two study stents per vessel or individual lesion length are allowed.; however, the total planned study stenting in the coronary tree cannot exceed 100 mm.

Subjects must sign an IRB approved Subject Informed Consent Form, and meet all the general and angiographic eligibility criteria before being enrolled to the trial.

6.3.1 Inclusion Criteria for Subject Selection

All inclusion criteria must be present for the patient to be eligible for enrollment.

6.3.1.1 General Inclusion Criteria

- 1. Age \geq 20 years.
- 2. Patient with an indication for PCI including angina (stable or unstable), silent ischemia (in absence of symptoms a visually estimated target lesion diameter stenosis of ≥70%, a positive non-invasive stress test, or FFR ≤0.80 must be present), NSTEMI, or recent subacute STEMI. For subacute STEMI the time of presentation to the first treating hospital, whether a transfer facility or the study hospital, must be >72 hours prior to enrollment and enzyme levels (CK-MB or Troponin) demonstrating that either or both enzyme levels have peaked.
- 3. Non-target vessel PCI are allowed prior to enrollment depending on the time interval as follows:

a. During Baseline Procedure:

- PCI of non-target vessels performed during the baseline procedure itself immediately prior to enrollment if successful and uncomplicated defined as: <50% visually estimated residual diameter stenosis, TIMI Grade 3 flow, no dissection ≥ NHLBI type C, no perforation, no persistent ST segment changes, no prolonged chest pain, no TIMI major or BARC type 3 bleeding.
- b. Less than 24 hours prior to Baseline Procedure:
 - i. Not allowed (see exclusion criteria #2).
- c. 24 hours-30 days prior to Baseline Procedure:

- i. PCI of non-target vessels 24 hours to 30 days prior to enrollment if successful and uncomplicated as defined above.
- ii. In addition, in cases where non-target vessel PCI has occurred 24-72 hours prior to the baseline procedure, at least 2 sets of cardiac biomarkers must be drawn at least 6 and 12 hours after the non-target vessel PCI.
- iii. If cardiac biomarkers are initially elevated above the local laboratory upper limit of normal, serial measurements must demonstrate that the biomarkers are falling.

d. Over 30 days prior to Baseline Procedure:

- i. PCI of non-target vessels performed greater than 30 days prior to procedure whether or not successful and uncomplicated.
- 4. Patient or legal guardian is willing and able to provide informed written consent and comply with follow-up visits and testing schedule.

6.3.1.2 Angiographic inclusion criteria (visual estimate)

- 5. Target lesion(s) must be located in a native coronary artery with visually estimated diameter of \geq 2.5 mm to \leq 4.25 mm.
- 6. Complex lesions are allowed including calcified lesions (lesion preparation with scoring/cutting and rotational atherectomy (e.g.: Rotablator System) and Directional Coronary Atherectomy, DCA) are allowed), presence of thrombus that is non-occlusive and does not require thrombectomy, CTO, bifurcation lesions (except for planned dual stent implantation), ostial RCA lesions, tortuous lesions, bare metal stent restenotic lesions, protected left main lesions.
- 7. Overlapping stents are allowed with the investigational device (MedJ-01).

6.3.2 Exclusion Criteria for Subject Selection

All exclusion criteria must be absent for the patient to be eligible for enrollment.

6.3.2.1 General Exclusion Criteria

- 1. STEMI within 72 hours (subacute) of initial time of presentation to the first treating hospital, whether at a transfer facility or the study hospital or patients in whom enzyme levels (either CK-MB or Troponin) have not peaked.
- 2. PCI within the 24 hours preceding the baseline procedure.
- 3. Non-target lesion PCI in the target vessel within 12 months of the baseline procedure.
- 4. History of stent thrombosis.
- 5. Cardiogenic shock (defined as persistent hypotension (systolic blood pressure <90 mm/Hg for more than 30 minutes) or requiring pressors or hemodynamic support, including IABP.
- 6. Subject is intubated.
- 7. Known LVEF <30%.

- 8. Relative or absolute contraindication to DAPT for 12 months (including planned surgeries that cannot be delayed).
- 9. Subject has an indication for chronic oral anticoagulant treatment (with either vitamin K antagonists or novel anticoagulants-NOACs
- 10. Calculated creatinine clearance <30 mL/min using Cockcroft-Gault equation
- 11. Hemoglobin <10 g/dL.
- 12. Platelet count <100,000 cells/mm³ or >700,000 cells/mm³.
- 13. White blood cell (WBC) count <3,000 cells/mm³.
- 14. Clinically significant liver disease.
- 15. Active peptic ulcer or active bleeding from any site.
- 16. Bleeding from any site within the prior 8 weeks requiring active medical or surgical attention.
- 17. If femoral access is planned, significant peripheral arterial disease which precludes safe insertion of a 6F sheath.
- 18. History of bleeding diathesis or coagulopathy or will refuse blood transfusions.
- 19. Cerebrovascular accident or transient ischemic attack within the past 6 months, or any permanent neurologic defect attributed to CVA.
- 20. Known allergy to the study stent components, whether in the MedJ-01 e.g. cobalt, nickel, chromium, Carbosil[®], PBMA, or limus drugs (ridaforolimus, zotarolimus, tacrolimus, sirolimus, everolimus, or similar drugs or any other analogue or derivative or similar compounds).
- 21. Known allergy to protocol-required concomitant medications such as aspirin, or DAPT (drugs that inhibit P2Y12 such as clopidogrel, prasugrel), or heparin, or iodinated contrast that cannot be adequately pre-medicated.
- 22. Any co-morbid condition that may cause non-compliance with the protocol (e.g. dementia, substance abuse, etc.) or reduced life expectancy to <24 months (e.g. cancer, severe heart failure, severe lung disease).
- 23. Patient is participating in any other investigational drug or device clinical trial that has not reached its primary endpoint or plans to participate in any clinical trial.
- 24. Women who are pregnant or breastfeeding (women of child-bearing potential, defined as females of childbearing potential if they have not undergone a permanent contraceptive operation or they are not postmenopausal, must have a negative pregnancy test within one week before treatment. Permanent contraceptive operation is defined as: hysterectomy, hysterosalpingectomy, or bilateral oophorectomy. The status of a female should be

considered as postmenopausal when she has not had a period for 12 consecutive months without an alternative medical cause).

- 25. Women who intend to procreate within 12 months after the baseline procedure (women of child-bearing potential who are sexually active must agree to use a reliable method of contraception from the time of screening through 12 months after the baseline procedure).
- 26. Patient has received an organ transplant or is on a waiting list for an organ transplant.
- 27. Patient is receiving or scheduled to receive chemotherapy within 30 days before or any time after the baseline procedure.
- 28. Patient is receiving oral or intravenous immunosuppressive therapy or has known lifelimiting immunosuppressive or autoimmune disease (e.g., HIV). Corticosteroids are allowed.

6.3.2.2 Angiographic Exclusion Criteria (visual estimate)

- 29. Target lesions in more than two (2) major coronary arteries (ie, two of LAD, LCX, RCA) and their respective branches. (The Ramus Intermedius is defined as a branch of the LCX).
- 30. More than two target lesions per target vessel are planned (two lesions separated by less than 10 mm that can be covered by a single stent are considered as one lesion).
- 31. More than 100 mm length of planned study stenting in the entire coronary tree.
- 32. Occlusive thrombus and/or a thrombus requiring thrombectomy in a target vessel.
- 33. Unprotected left main lesions \geq 30%, or planned unprotected left main intervention.
- 34. Ostial LAD or LCX lesions (stenting of any diseased segment within 5 mm of the unprotected left main coronary artery).
- 35. Bifurcation lesions with planned dual stent implantation.
- 36. Stenting of lesions due to DES restenosis.
- 37. Another lesion in a target or non-target vessel (including all side branches) is present that requires or has a high probability of requiring PCI within 12 months after the baseline procedure.
- 38. Target lesion exists in bypass graft vessels.

6.3.3 Criteria and Procedures for Subject Withdrawal or Discontinuation

6.3.3.1 When and How to Withdraw Subjects

Each enrolled subject shall remain in the trial until completion of the required follow-up period. However, a subject's participation in any clinical trial is voluntary and the patient has the right to withdraw at any time without penalty or loss of benefit. Conceivable reasons for discontinuation may include, but not be limited to, the following:

- Subject voluntary withdrawal
- Subject withdrawal by physician as clinically indicated
- Subject lost-to follow-up

The reason for subject discontinuation must be documented on the CRF and source documents. The Primary Investigators must also report all subject discontinuations to their IRB as defined by their institution's procedure.

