6.3.3.2 Data to Be Collected from Withdrawn Subjects

All data from evaluations and treatments performed prior to the withdrawal should be documented on the CRFs. Source documents and angiograms that pre-date the withdrawal should be submitted as required by the clinical investigation plan. No data that post-dates the withdrawal will be collected.

[figure not shown]

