6.3.3.3 Follow-up for Withdrawn Subjects

Once a subject has withdrawn from the trial, no further follow-up contact will be performed. However, vital status will be obtained from public records.

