6.4.3.1 De-registered Subjects

In case of de-registration, the de-registered subjects will be followed until resolution of any adverse event related to study procedures (refer to instructions for de-registration in the trial's Site Binder).

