14.3.4 Unanticipated Serious Adverse Device/Drug Effect (USADE)

An SADE is an effect which by its nature, incidence, severity or outcome has not been identified in the current version of the risk analysis report, IB, or labeling.

Adverse Events	Non-device related	Device-, Drug- or	procedure-related	
Non-serious	Adverse Event (AE) ^a		ce/Drug Effect DE)	
		Serious Adverse Device/Drug Effect (SADE)		
Contours	Serious Adverse Event	Anticipated	Unanticipated	
Serious	(SAE) ^b	Anticipated Serious	Unanticipated Serious	
		Adverse Device/Drug	Adverse Device/Drug	
		Effect (ASADE)	Effect (USADE)	
a Includes all categories				
b Includes all categories that are serious				

Table 8: Categories of Adverse Events

14.4 Time Period in Which the Investigator Shall Report All AE and Device Deficiencies to the ICCC (Quintiles)

Each complication meeting the definition for SAE or device deficiency will be reported upon discovery to the ICCC (Quintiles) and within 24 hours of the Investigator's knowledge of the event. The Investigator will further report the event or device deficiency to the IRB according to the institution's IRB reporting requirements. The subject's course must be monitored until the event has subsided or, in a case of permanent impairment, until the event stabilizes and the overall clinical outcome has been ascertained.

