14.5 Details of Process for Reporting AE and Device Deficiencies

14.5.1 **Reporting AE and Device Deficiencies**

The Investigator will monitor the occurrence of adverse events or device deficiencies for each subject during the course of the trial. All adverse events (AEs) reported by the subject, observed by the Investigator, or documented in medical records will be recorded on the adverse event CRF, whether believed by the Investigator to be related or unrelated to the study stent and drug constituting the stent. Starting with the trial enrollment, any new event/experience that was not present at screening, or worsening of an event presents at baseline, is considered an adverse event. All adverse events will be monitored until they are adequately resolved or stabilized.

Unchanged, chronic conditions are not adverse events and should not be recorded on the adverse event CRF. All unanticipated adverse device/drug effects and cardiac related serious adverse events will be collected and monitored throughout the entire course of the trial. Non-cardiac SAEs and AEs will be collected and monitored throughout the trial, i.e. until 5 years from enrollment.

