14.10.7 Follow-up of Subjects after Adverse Events

Subjects should be followed after adverse events until resolution or until end of trial, whichever comes first. Additional trial visits may be scheduled as necessary to allow for adequate follow-up.

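### Withdrawal by a physician ends all contact and data collection, which conflicts with the adverse-event follow-up rules and leaves possibly outcome-related gaps in TLF that no planned analysis examines

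*Protocol*

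**What the plan says.** Protocol 6.3.3.1 opens with a retention rule: "Each enrolled subject shall remain in the trial until completion of the required follow-up period". It then gives conceivable reasons for discontinuation: the subject's own decision, "Subject withdrawal by physician as clinically indicated", and loss to follow-up. The physician ground is not defined and is not confined to the time before implantation.

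Two rules follow for withdrawn subjects, and neither depends on who decided. Section 6.3.3.2 says "No data that post-dates the withdrawal will be collected". Section 6.3.3.3 says "Once a subject has withdrawn from the trial, no further follow-up contact will be performed", and adds that vital status will still be taken from public records.

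The adverse-event rules make no exception for withdrawn subjects:
- Section 14.4, on SAEs and device deficiencies: "The subject's course must be monitored until the event has subsided", or until it stabilizes where impairment is permanent.
- Section 14.5.1, on all adverse events: "All adverse events will be monitored until they are adequately resolved or stabilized".
- Section 14.10.7: "Subjects should be followed after adverse events until resolution or until end of trial, whichever comes first".

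Section 6.4.3.1 covers patients removed because the stent could not be implanted for reasons unrelated to the device: "the de-registered subjects will be followed until resolution of any adverse event related to study procedures".

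SAP 15 and 15.1.2 keep in the primary analysis only patients with at least 335 days of follow-up or a TLF event by day 379. SAP 8.3 rules out imputation of missing outcomes. The only sensitivity analysis of the primary endpoint (SAP 15.1.3) repeats it in the Per Protocol Set. Time-to-event endpoints are censored at withdrawal (SAP 15.2.2.2).

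**The concern.** A physician who withdraws an implanted subject while an SAE is open leaves the site with two incompatible instructions: stop all contact, and keep monitoring the event. A de-registered patient, who has no study stent, is followed until procedure-related events resolve. On paper that patient gets more event follow-up than an implanted subject withdrawn by a physician.

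The second issue is the primary endpoint. A withdrawal made on clinical grounds, in an open-label trial, by someone who knows the patient's course, may be related to the risk of TLF. If the subject has had no TLF event and leaves before day 335, the SAP removes that subject from the denominator. A later target-vessel MI or TLR is then never recorded, and no planned analysis asks whether the conclusion depends on such subjects.

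**Working it through.** **Text comparison for a physician-withdrawn subject with an open SAE**
- Contact: none under 6.3.3.3, but 14.4 requires monitoring until the event subsides or stabilizes. Direct conflict.
- Data: none after withdrawal under 6.3.3.2, but 14.5.1 requires all adverse events to be monitored until resolved or stabilized. Direct conflict.
- 14.10.7 stops at resolution or end of trial. If end of trial means the whole study, it conflicts; if it means the subject's own exit, it does not. Arguable.
- 6.3.3.2 bars any later data, while 6.3.3.3 obtains vital status. These two sections conflict with each other.

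**What is lost and what is kept**
- Lost: later MI, TLR and non-fatal adverse events.
- Kept: a TLF event before withdrawal (SAP 15), and adverse events already recorded, since the subject remains in the Safety Analysis Set.
- Unclear: a later death. Vital status may reveal it, and Protocol 21.1 treats deaths as cardiac unless a non-cardiac cause is unequivocal. The SAP does not say whether such a death enters TLF.

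**Illustration of sensitivity**

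The plan gives no expected number of physician withdrawals, so there is no plan figure to reproduce. The inputs come from Protocol 7.5 and SAP 15.1.2: 100 subjects with 5% loss, so 100 × 0.95 = 95 evaluable; 4:1 matching, so 4 × 95 = 380; assumed TLF rate 0.058, so 0.058 × 380 = 22.04, taken as 22 events; margin 0.05; one-sided alpha 0.10.

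The printed statistic is τ = (p1 − p2 − 0.05) / √[p1(1 − p1)/n1 + p2(1 − p2)/n2], with p2 = 22/380 = 0.05789.
- 7/95: p1 = 0.07368, difference 0.01579, SE 0.02936, τ = −0.03421/0.02936 = −1.17, p = 0.122. Fails.
- 6/94: p1 = 0.06383, difference 0.00594, SE 0.02791, τ = −0.04406/0.02791 = −1.58, p = 0.057. Passes.

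Sections 7.2.1 of the protocol and 15.1.2 of the SAP name the test Farrington-Manning, which usually takes its variance from the restricted maximum-likelihood estimates under the null. With that variance:
- 7/95: SE 0.03336, z = −0.03421/0.03336 = −1.03, p = 0.153. Fails.
- 6/94: SE 0.03334, z = −0.04406/0.03334 = −1.32, p = 0.093. Passes.

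The second line in each pair is the same trial with one of the seven event patients withdrawn before the event. The comparator was held at 22/380; reducing it to 22/376 (4 × 94) gives a difference of 0.06383 − 0.05851 = 0.00532, SE 0.02797, τ = −0.04468/0.02797 = −1.60, p = 0.055, so that choice does not matter.

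Neighbouring counts under the restricted variance: 6/95 gives p = 0.089 (passes) and 8/95 gives p = 0.240 (fails). At a true count of six the test passes already. At eight, hiding one event leaves seven, 7/94, which still fails (difference 0.01657, SE 0.03354, z = −1.00, p = 0.160). One hidden event therefore reverses the result only at exactly seven. At a true rate of 5.8%, the chance of exactly seven events in 95 is about 13%.

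**The case against.** The strongest reply is that this is a narrow wording conflict and that the protocol limits the damage. Much of that stands.

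- Events before withdrawal are well protected. Every MI, unscheduled revascularization and stent thrombosis is an SAE (14.3.1), reportable within 24 hours (14.4). The reason for discontinuation must be documented and reported to the IRB (6.3.3.1), and the DSMB reviews adverse events (14.9).
- Vital status is still obtained, so the gravest TLF component may be known.
- A reader might infer that no study treatment remains after implantation, so that a physician ground has no purpose. The documents do not support that: staged stenting is allowed within six weeks (6.4.4) and dual antiplatelet therapy runs for at least 12 months (6.4.9.3).
- A reader might infer that every adverse event must be followed to resolution. Section 14.5.1 also accepts stabilization, and 14.10.7 accepts end of trial.
- A reader might infer that a subject lost after a missed call may not be contacted again. The no-contact sentence speaks of a subject who has withdrawn. Whether it covers lost subjects is not clear, and nothing says that one missed call makes a subject lost.
- The conflict with the adverse-event rules also arises when a subject withdraws voluntarily. There, however, the subject's right to refuse contact explains the stop. A physician's decision does not supply that reason.

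What the reply does not remove is the conflict of 6.3.3.2 and 6.3.3.3 with 14.4 and 14.5.1, or the lack of any analysis of missing TLF outcomes.

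**Conclusion.** The point holds as a conflict in the protocol and a gap in the SAP. Physician withdrawal ends contact and data collection while 14.4 and 14.5.1 still require open events to be monitored. Subjects who leave before day 335 without a TLF event vanish from the primary analysis without imputation or a relevant sensitivity analysis.

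The size of any bias cannot be estimated. It would be tempting to say that the clause removes sicker patients, or that one withdrawal will reverse the trial. The documents state neither. That such withdrawals may be related to outcome is an inference from the clinical ground and the open-label design. The reversal from 7/95 to 6/94 rests on an assumed 22/380 comparator and occurs, for a single hidden event, only at seven events. It shows that the result can be fragile and does not forecast the effect of the clause. The change is worth making because it is cheap and prevents avoidable missing outcomes.

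**What to change.** **Protocol 6.3.3.1 to 6.3.3.3**
- Limit the end of data collection and contact to the subject's own withdrawal of consent.
- State that a physician's decision to stop protocol-directed care does not end scheduled follow-up, including telephone visits. This concerns observation only and leaves care decisions untouched.
- Make clear that the no-contact rule does not apply to subjects recorded as lost.
- Ask a subject who withdraws consent with an open SAE or device-related adverse event to agree to follow-up of that event.
- Reconcile 6.3.3.2 with the vital-status sentence in 6.3.3.3, and both with 14.4, 14.5.1 and 14.10.7.

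**SAP**
- State whether and how a death found through vital status after withdrawal enters TLF.
- Add a sensitivity analysis of TLF for subjects without 335 days of follow-up and without an event, for example counting them as events, or a tipping-point analysis.

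The cost is a few additional contacts of a kind already scheduled, a line in the consent form, and one extra analysis.
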